  4. EKG
  5. Serum Chemistry and Hematology
  6. Serum HGF if discontinued prior to Day 90
  7. Copies of VM202 in whole blood if discontinued prior to Day 90
  8. Injection site reaction assessment if discontinued prior to Day 60
  9. Adverse Events

In case of a subject lost-to-follow-up, the Investigator must do his/her best to contact the subject (by phone or letter) at least twice. If no response is obtained from the subject, the Investigator is encouraged to contact one of the subject's relatives or his/her general practitioner. Documentation of these contacts must be recorded in the subject medical chart. It can be, for instance, the acknowledgement of receipt of a letter sent to the subject.

### **3.5.3. PREMATURE STUDY TERMINATION**

---

The Sponsor reserves the right to discontinue the study for any safety, ethical or administrative reason at any time.

---

## **3.6. INVESTIGATIONAL DRUG PRODUCT AND ACCOUNTABILITY**

---

### **3.6.1. INVESTIGATIONAL DRUG PRODUCT**

---

VM202 is a DNA plasmid which contains a novel genomic cDNA hybrid human hepatocyte growth factor (HGF) coding sequence (HGF-X7) expressing two isoforms of HGF, HGF728 and HGF723. The key feature of HGF-X7 is that it was designed by inserting a series of intron sequences into certain sites of HGF cDNA so that both isoforms of HGF protein are expressed simultaneously and efficiently as in the human genome. Because there is no change in the coding region of the HGF gene, HGF proteins generated from VM202 are identical to the wild-type human HGF proteins.

The plasmid has 7,377 base pairs, a HCMV enhancer / promoter, a growth hormone polyadenylation terminator sequence, ColEI originator, and the Kanamycin resistance gene, on a pCK backbone.

VM202 is supplied in a sterile glass vial containing 2.5 mg of lyophilized study product. VM202 should be stored in a refrigerator at temperatures between 2° C and 8° C in an appropriately locked room accessible only to the pharmacist, or a duly designated person. Since VM202 does not contain preservatives, opened vials of VM202 and VM202 reconstituted with water for injection (WFI) must be used

---

within 6 hours when stored at room temperature. VM202 should never be frozen. A complete description of test article administration can be found in [Appendix 4](#).

### **3.6.2. PRODUCT ACCOUNTABILITY**

---

In accordance with federal regulations (21CFR 312.62), all Investigators are required to keep accurate records showing final disposition of all investigational drugs.

Investigational drugs are to be used only in accordance with this protocol and under supervision of the Study Pharmacist or a duly designated person. The Study Pharmacist or his/her designee will maintain an accurate record of the receipt of the test drug as shipped by the Sponsor / Designee, including the date received. In addition, an accurate drug disposition record will be kept, specifying the amount dispensed to each subject and the date of dispensation. This inventory record must be available for inspection at any time. Copies of this record will be provided to the Sponsor by the Study Pharmacist at the conclusion of the study.

After the study is completed, the Study Pharmacist must account for all drug used, unused and partially used. Unused study medication from the study site will be returned to the Sponsor / Designee as directed in writing by the Sponsor for gross reconciliation.

### **3.6.3. DOSE AND ADMINISTRATION**

---

VM202 is supplied in a sterile glass vial containing 2.5 mg of lyophilized study product. Before administration, it will be reconstituted with 5 mL of water for injection (WFI) by the study pharmacist for a final VM202 concentration of 0.5 mg / mL. Each reconstituted vial is only to be used for one subject. A complete description of test article administration can be found in [Appendix 4](#).

---

## **3.7. PRIOR AND CONCOMITANT MEDICATION**

---

All concomitant medications (taken within 30 days of the first injection) will be recorded on the CRF at each study visit. For each medication taken, the following information will be collected:

- Medication trade name;
  - Indication for which the medication was given;
  - Dose/strength, route, and frequency of administration;
  - Date started and date stopped (or continuation at study exit).
-

---

## 4. EXAMINATIONS AND EVALUATIONS

---

### 4.1. EVALUATIONS CONDUCTED AT BASELINE ONLY

---

#### 4.1.1. MEDICAL HISTORY

---

A medical history will be obtained at Screening/Baseline. All positive findings will be carefully documented on the CRF. Any new finding discovered during screening and prior to the first study drug administration (Day 0) will be considered to be part of the medical history and will not be recorded as an adverse event.

The Investigator will confirm the diagnosis of ALS using the revised El Escorial / Airlie House diagnostic criteria.

#### 4.1.2. PHYSICAL EXAM

---

A physical exam will be performed at Screening and at 9 months. The exam will include the following: head, eyes, ears, nose, and throat (HEENT), heart, lungs, abdomen, extremities, lymph nodes, and musculoskeletal, neurological, gastrointestinal, and dermatological systems. Any clinically significant abnormalities should be recorded in the subject's CRF.

#### 4.1.3. VIRAL SCREENING

---

The local laboratory will be responsible for Screening viral testing and assays to include: HIV-1, HIV-2, HTLV, and active HBV and HCV as determined by Hepatitis B core antibody (HBcAb), antibody to Hepatitis B antigen (IgG and IgM; HBsAb), Hepatitis B surface antigen (HBsAg) and Hepatitis C antibodies (Anti-HCV).

#### 4.1.4. 12-LEAD EKG

---

A 12 lead electrocardiogram (EKG) will be conducted at Screening and at 9 months. The EKG recording will be printed out, and a copy will be placed with subject records. Any (clinically significant) abnormalities will be documented.

#### 4.1.5. PREGNANCY TEST (WOMEN OF CHILDBEARING POTENTIAL ONLY)

---

For women of childbearing potential, a urine beta human chorionic gonadotropin ( $\beta$ -HCG) test will be performed at Screening. Results of the test must be negative and effective contraception documented. Acceptable methods of contraception include:

- Barrier type devices (*e.g.*, female condom, diaphragm and contraceptive sponge) used only in combination with a spermicide;
- Intrauterine device;
- Oral contraceptive agents;
- Depo-provera (medroxyprogesterone acetate);
- Levonorgestrel implants;

Abstinence, the rhythm method and / or contraception by a partner are not considered acceptable methods of contraception.

---

---

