### 3.2. STUDY DESIGN

This is a phase I/II, open label, single center study designed to assess the safety and tolerability of intramuscular injections of VM202 in patients with ALS. Subjects with ALS will be screened for study eligibility after giving informed consent.

**Screening.** Using the revised El Escorial / Airlie House diagnostic criteria and medical history, subjects will be confirmed as having ALS < 2 years. If applicable, the subject will be washed out of prohibited medication (see [section 3.4.4](#)). During medication wash-out, screening procedures consisting of assessment of study eligibility, a medical history, vital signs, physical exam, concomitant medications, ALSFRS-R, viral screening, 12 lead EKG, FVC, serum chemistry and hematology, and (urine) pregnancy test (for women of childbearing potential only) will be performed.

All screening assessments should occur within the 30 days prior to Day 0 (day of first injections).

**Injection.** Prior to injections on Day 0, subjects will be assessed using the ALSFRS-R, the Medical Research Council (MRC) scale for muscle strength testing, dynamometry, FVC, and muscle circumference. These tests can be conducted one day before the scheduled injection visit. Immediately before injection on Day 0, the following will be conducted: recording of concomitant medications, vital signs, and blood draw for serum chemistry and hematology, serum HGF and copies of VM202 in whole blood.

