VM202 will be delivered in 0.5 mL intramuscular injections of a solution of 0.5 mg VM202 / mL. It will be administered over the course of four visits: Day 0, Day 7, Day 14, and Day 21. As in all previous VM202 studies, final dose of VM202 for each target muscle group is divided and administered 2 weeks apart. However, in order to reduce the injection burden on the ALS patient, injection of the upper limbs will be done on separate visits from injection of the lower limbs. The first eligible subject will begin with the lower limb injection series and will be injected in accordance with the schedule outlined in [Table 3](#). The next sequentially eligible patient will begin with injection of the upper limbs (see [Table 4](#)). Subsequent eligible patients will be treated in an alternating fashion, such that 9 patients will have initiated their VM202 injections in the lower limbs and 9 patients will have initiated their VM202 injections in the upper limbs. ***Please note: Regardless of injection order, all subjects will receive the same final dose of VM202 and the same number of injections per muscle group.***

---

[REDACTED]

[REDACTED]

Serum chemistry and hematology will be determined on Day 0, Day 30, Day 90 and 9 months.

FVC, ALSFRS-R, and muscle strength (MRC scale) will be assessed at Day 0, Day 30, Day 60, Day 90, at 6 months and 9 months. Muscle circumference and dynamometry will be ascertained on Day 0, Day 60, Day 90, at 6 months, and 9 months.

Concomitant medications and vital signs will be recorded throughout the 9 month follow-up period. Adverse events will be assessed starting on Day 0 throughout the 9 month follow-up period, and injection site reactions will be assessed starting on Day 0 through Day 60. Study enrollment will be staged. Enrollment will be halted after the sixth subject qualifies for treatment. A Data Safety Monitoring Board (DSMB) will conduct a safety evaluation after the first patient treated completes the Day 60 follow-up evaluation and the five other sequentially enrolled subjects complete at least the Day 30 follow-up. Enrollment will be suspended until a formal recommendation to proceed (or not proceed) is made by the DSMB.

The study will be suspended pending DSMB review if any of the following SAEs are attributed to VM202 injections during any time during the study:

- acute anaphylaxis (including erythema, hives, wheezing, stridor or respiratory distress);

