### 3.3.1. INCLUSION CRITERIA

---

Subjects must satisfy all of the following criteria to be included in the study:

1. Age  $\geq$  21 years, but  $\leq$  75 years
2. Subjects diagnosed with:
  - clinically definite ALS,
  - clinically probable ALS, or
  - clinically probable-laboratory supported ALS;as specified in the revised El Escorial / Airlie House diagnostic criteria
3. Onset of ALS  $<$  2 years at Screening;
4. Forced Vital Capacity (FVC)  $\geq$  60% of predicted;
5. Revised Amyotrophic Lateral Sclerosis Functional Rating Scale (ALSFRS-R)  $\geq$  30;
6. Not taking riluzole, or on a stable dose for at least thirty days prior to Screening (defined as no noted toxicities);
7. Able and willing to give informed consent;
8. If female of childbearing potential, negative urine pregnancy test at Screening and using acceptable method of birth control during the study.

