### 3.3.2. EXCLUSION CRITERIA

---

Subjects *will not be eligible for the study* if any of the following criteria are present:

1. Neurological symptom(s) due to vitamin B12 deficiency;
2. Requires tracheotomy ventilation or noninvasive ventilation  $>$  16 hours / day;
3. Comorbidities such as Parkinson's disease, schizophrenia, renal failure, or any other severe complication that, in the Investigator's opinion, will compromise the safety of the patient or confound interpretation of the data collected in this study;
4. Other neuromuscular disease;
5. Inflammatory disorder of the blood vessels (inflammatory angiopathy, such as Buerger's disease);
6. Active infection;
7. Chronic inflammatory disease (e.g., Crohn's disease, rheumatoid arthritis);
8. Positive HIV or HTLV at Screening;
9. Active Hepatitis B or C as determined by Hepatitis B core antibody (HBcAb), antibody to Hepatitis B surface antigen (IgG and IgM; HBsAb), Hepatitis B surface antigen (HBsAg) and Hepatitis C antibodies (Anti-HCV) at Screening;
10. Subjects with known immunosuppression or currently receiving immunosuppressive drugs, chemotherapy or radiation therapy;
11. Stroke or myocardial infarction within last 3 months;
12. Patients with a recent history ( $<$  5 years) of malignant neoplasm except basal cell carcinoma or squamous cell carcinoma of the skin (if excised and no evidence of recurrence);

- 
13. Subjects requiring > 81 mg daily of acetylsalicylic acid; subjects may be enrolled if willing/able to switch to ≤ 81 mg daily of acetylsalicylic acid or to another medication;
  14. Subjects requiring regular COX-2 inhibitor drug(s) or non-specific COX-1/COX-2 inhibiting drugs, or high dose steroids (excepting inhaled steroids); subjects may be enrolled if willing/able to undergo medication wash-out prior to the first dosing and to refrain from taking these drugs for the duration of the study;
  15. Have used an investigational drug within 30 days of Screening;
  16. Pregnant or currently lactating;
  17. Major psychiatric disorder in past 6 months;
  18. Known drug or alcohol dependence or any other factors which will interfere with the study conduct or interpretation of the results or who in the opinion of the Investigator are not suitable to participate.
- 

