### **3.4.3. SCREENING (DAY -30 TO DAY 0)**

Prior to full screening, subjects will give informed consent. If applicable, the subject will be washed out of prohibited medication (see [section 3.4.4](#)). Subject eligibility will be assessed as follows:

- Evaluation of Eligibility Criteria
- Medical History
- Physical Exam
- Viral screening – HIV, Anti-Human T-Cell Lymphotropic Virus (HTLV), Active Hepatitis B or C as determined by Hepatitis B core antibody (HBcAb), antibody to Hepatitis B antigen (IgG and IgM; HBsAb), Hepatitis B surface antigen (HBsAg) and Hepatitis C antibodies (Anti-HCV)
- EKG
- Urine pregnancy test (for women of childbearing potential only)
- Concomitant Medications
- Vital Signs, including height
- Serum chemistry and hematology
- FVC
- ALSFRS-R

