#### **3.4.5. TREATMENT AUTHORIZATION**

After providing written informed consent, potential study participants will undergo Screening assessments. The site will complete a Treatment Authorization Form (TAF) for subjects determined to be eligible for study participation. The TAF includes the subject identification number, demographic information (gender, date of birth), date of informed consent and indication that the subject meets all inclusion and exclusion criteria. The completed TAF will be faxed to the Sponsor or its designee. The Sponsor or its designee will confirm whether the subject can be treated and assign the Injection Schedule. Upon receipt, the Investigator or designee will

---

schedule the subject to undergo the study treatment. Note: adherence to this process is mandatory to track enrollment and to confirm initial treatment.

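### Pregnancy is an exclusion, but the only scheduled test is at Screening, so the negative result may be up to 30 days old at the first injection and up to 52 at the last

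*Combined protocol and SAP*

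**What the plan says.** Exclusion criterion 16 (Section 3.3.2, repeated in the synopsis) reads "Pregnant or currently lactating". Inclusion criterion 8 (Section 3.3.1) reads "If female of childbearing potential, negative urine pregnancy test at Screening and using acceptable method of birth control during the study".

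Section 4.1.5 specifies a urine beta-HCG: the "test will be performed at Screening. Results of the test must be negative and effective contraception documented". It lists the accepted contraceptive methods: barrier devices count only with a spermicide, and abstinence, rhythm and a partner's contraception do not count. The section sits under the heading "EVALUATIONS CONDUCTED AT BASELINE ONLY".

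The Screening list in Section 3.4.3 includes "Urine pregnancy test (for women of childbearing potential only". Appendix 1 gives the test one tick, in the Screening / Baseline column. The pre-injection lists (Sections 3.4.6.1, 3.4.6.2, 3.4.7.1, 3.4.8.1 and 3.4.9.1) do not contain it, and the laboratory schedule in Appendix 1 has no pregnancy row.

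On timing, Section 3.2 states "All screening assessments should occur within the 30 days prior to Day 0 (day of first injections" and, of VM202, "It will be administered over the course of four visits: Day 0, Day 7, Day 14, and Day 21". Under Section 3.4.5 the Treatment Authorization Form, sent to the sponsor before treatment is scheduled, carries the "date of informed consent and indication that the subject meets all inclusion and exclusion criteria".

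**The concern.** Pregnancy status can change between Screening and dosing. The plan makes it an exclusion, tests it once, and has no scheduled assessment that confirms it when the product is first given. A subject could therefore meet exclusion 16 at first exposure and still be injected with a gene-transfer product, without any departure from the protocol.

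A gap between test and dose is likely in practice. After Screening the site completes the authorization form, faxes it, waits for the sponsor to confirm and assign the injection schedule, and only then books treatment (Section 3.4.5). For subjects who must stop a prohibited drug, Screening procedures run during the wash-out (Section 3.2), which Appendix 3 mostly sets at 1 or 2 weeks.

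What is at stake is subject safety and whether an entry criterion is verified at the point where it matters. No estimate or test is affected: Section 6 plans no hypothesis testing.

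**Working it through.** The documents state no test-to-dose interval, so there is no plan figure to reproduce. The check is calendar arithmetic on the visit windows.

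**Inputs**
- Screening window: Day -30 to Day 0 (Sections 3.2 and 3.4.3; synopsis schedule).
- Injection visits: Day 0; Day 7 ± 1; Day 14 ± 1; Day 21 ± 1 (synopsis schedule; Sections 3.4.6 to 3.4.9).
- Pregnancy tests after Screening: none (Appendix 1 and the pre-injection lists).

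**Formulas**
- Longest gap = (injection day + upper visit window) - (-30).
- Nominal gap from a Day -30 test = injection day - (-30).
- Shortest gap, if the test is done on Day 0 = injection day - lower visit window.

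| Injection | Longest gap (days) | Nominal gap from Day -30 (days) | Shortest gap (days) |
|---|---|---|---|
| 1 (Day 0) | 0 + 30 = 30 | 30 | 0 |
| 2 (Day 7) | 7 + 1 + 30 = 38 | 37 | 7 - 1 = 6 |
| 3 (Day 14) | 14 + 1 + 30 = 45 | 44 | 14 - 1 = 13 |
| 4 (Day 21) | 21 + 1 + 30 = 52 | 51 | 21 - 1 = 20 |

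The age of the negative result thus ranges from 0 to 30 days at the first injection and from 20 to 52 days at the last. The 52 uses the +1 day window; on nominal days it is 51.

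**After the fix.** With a test in the Day 0 pre-dose list, the first-injection gap falls from at most 30 days to the same visit. The longest gap to the last injection becomes 21 + 1 - 0 = 22 days.

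**Comparison with other Screening measures.** Day 0 repeats FVC, ALSFRS-R, vital signs, serum chemistry and hematology. It does not repeat the EKG or the physical exam, which return only at 9 months or at early withdrawal.

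**The case against.** The strongest answer is that the plan is consistent and has a safeguard. Every visible section places one test at Screening, and criterion 8 ties the negative result to Screening, so a reader who infers that the protocol contradicts itself goes too far. This is a gap in design. Criterion 8 also makes contraception a continuing duty, and Section 4.1.5 is strict about methods. That stands and lowers the risk materially. It does not establish status at dosing: no minimum time on a method before the test or before Day 0 is stated, and no Day 0 item asks about contraception. The concomitant-medication record might show a hormonal method but would not show barrier use.

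Three stronger inferences should be resisted.

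- That pregnancy is singled out because all other changeable Screening measures are repeated at Day 0. The EKG and physical exam are not, and nothing says the Day 0 FVC and ALSFRS-R serve as an eligibility re-check.
- That eligibility is closed once the authorization form is sent, or that nothing could bring a pregnancy to light. Section 3.4.5 says only that the form records that the criteria are met. Section 3.5.2 lets the investigator discontinue a subject on health grounds at any time, and adverse events are reviewed before the second, third and fourth injections. These are weaker than a test, but they exist.
- That the harm is known to be large. The results of the reproductive-tissue work in Section 1.6 are not visible, and Section 1.7.4 describes rapid elimination from the circulation.

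The consent pages were removed and part of Section 3.2 is redacted, so wording on repeat testing there cannot be ruled out. The visit lists and Appendix 1, from which a site works, contain none.

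**Conclusion.** The point holds as a design gap that should be closed. The plan excludes pregnant subjects but verifies this once, on a result that may be up to 30 days old at the first injection and up to 52 days old at the last. Both are upper limits and shrink if the test is done nearer Day 0.

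The conclusion rests on the visit windows as written and on the absence of any repeat test in the visible text. It needs no assumption about how many of the 18 subjects are women of childbearing potential or how probable a pregnancy is; neither is stated. Given the contraception requirement and the small sample, the event is likely rare. The case for acting is that an existing criterion can be verified at first exposure at very little cost.

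**What to change.** Reconcile exclusion 16 and criterion 8 with the assessment schedule, so that eligibility is verified at first exposure:

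- List the urine test the protocol already specifies, for women of childbearing potential, among the Day 0 pre-dose assessments in Section 3.4.6.2, Section 4.1.5 and the Day 0 pre-dose column of Appendix 1.
- Align criterion 8 in Section 3.3.1 and in the synopsis, so that the negative result is required at Screening and before injection on Day 0.
- State whether exclusion 16 also applies at Days 7, 14 and 21, and make Sections 3.4.7.1, 3.4.8.1 and 3.4.9.1 and Appendix 1 consistent with that answer. This decision belongs to the sponsor; no dosing or stopping rule is proposed here.

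The cost is one urine strip and one CRF field per such subject at a visit that already has pre-dose sampling, with no added visit or staff. A Day 0 test can still miss a very recent conception, so it narrows the gap without removing it.

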## 4.2. EVALUATIONS CONDUCTED THROUGHOUT THE STUDY

### 4.2.1. CONCOMITANT MEDICATIONS

Concomitant medications will be recorded at Screening and at each visit using the trade name or generic name as described in [Section 3.7](#).

### 4.2.2. VITAL SIGNS

Vital signs consisting of blood pressure (while subject is sitting), temperature, body weight, heart rate, and respiratory rate will be measured and recorded at Screening and at every visit through the 9 month follow-up. Body weight need only be measured once during injection visits (Day 0, Day 7, Day 14, Day 21). All other vital sign measurements will be made both pre and post injection.

